## Clinical Investigation Plan

Activity	Enrollment / Baseline	Procedure (~14-days of consent)	Pre-Discharge (<72 hrs post-proc.)	7-14 Day Phone Call or In-Person (7-14 days)	3-Month In-Person (91±21 days)	6-Month In-Person (181±30 days)	12-Month In-Person (365±30 days)	15-Month In-Person (450±30 days)
Ablation procedure		X						
Assess for Pericardial Effusion		X 						
Monthly Event Recording					X 	X 	X 	X 
Adverse Event Assessment	X	X	X	X	X	X	X	X
Document Deviations	(X)	(X)	(X)	(X)	(X)	(X)	(X)	(X)
Withdrawal	(X)	(X)	(X)	(X)	(X)	(X)	(X)	(X)

(X) If applicable

1. A neurological assessment is recommended to be performed as outlined in the 2017 Consensus Statement.
2. Either a 24-hr Holter or 2 ECGs obtained ≥7 days apart may be used to demonstrate continuous AF at Baseline.
3. Thrombus assessment must be performed the day prior to or on the day of the procedure. If a thrombus is discovered, the procedure should be postponed and the subject placed on anticoagulation until the thrombus is resolved as confirmed by imaging.
4. Imaging must be performed prior to the conclusion of the procedure to exclude pericardial effusion.
5. 24-hour Holters must be obtained at the 6-month and 15-month follow-up visits. It is recommended that a 24-hour Holter be obtained at the 3-month and 12-month follow-up visits.
6. It is recommended that event recordings are collected monthly after the initial ablation procedure and whenever the subject is experiencing a symptomatic episode starting at 3-months to 15-months post-procedure as noted in the 2017 Consensus Statement.

### 6.8 Core Laboratory

A core lab will be used for the collection, interpretation, and collation of data obtained from the following sources:

- 24-hour Holter monitoring at the 6-month and 15-month follow-up visits

The core lab will provide independent review of this data by appropriately trained personnel using standardized procedures to interpret Holter tracings for adjudication of atrial arrhythmias. Findings will be communicated to the investigator and to the Sponsor. The core lab's adjudication findings will be used for analysis.

### 7.0 Adverse Events

To comply with worldwide standards and guidelines on clinical investigation adverse event reporting, the Sponsor has adopted uniform and worldwide applicable standard definitions and reporting timelines to be used and adhered to by the investigators.

Determination of whether there is a reasonable possibility that the device under investigation caused or contributed to an AE is to be **determined by the Investigator** and recorded on the appropriate CRF form. Determination should be based on assessment of temporal relationships, evidence of alternative etiology, medical/biologic plausibility, and patient condition (pre-existing condition).

## Clinical Investigation Plan

### 7.1 Adverse Event Definitions and Reporting

#### 7.1.1 Adverse Event

An adverse event (AE) is any untoward medical occurrence, unintended disease or injury, or untoward clinical signs (including abnormal laboratory findings) in subjects, users or other persons, whether or not related to the medical device under investigation. This definition includes events related to the medical device under investigation and includes events related to the procedures involved.

##### 7.1.1.1 Adverse Event Reporting

Safety surveillance and reporting starts as soon as the patient is enrolled in the clinical investigation (after consent is obtained and all eligibility criteria are met). Safety surveillance and reporting will continue until the last follow-up visit has been performed, the subject is deceased, the subject concludes participation in the clinical investigation or the subject withdraws from the clinical investigation. All adverse event data, including deaths, will be collected throughout the time period defined above and will be reported to the Sponsor on a CRF. Additional information with regard to an adverse event should be updated within the appropriate CRF.

For the purposes of this study, the following adverse events will be reported:

- Adverse events that are assessed by the investigator as being related to either the ablation catheter or the ablation procedure will be reported in the database, preferably within 7-days of the site learning of the event
- Serious adverse events, regardless of relatedness to the procedure and/or the ablation catheter will be reported as described in **Section 7.1.2.1**.

Recurrence of AF, AFL, or AT are not considered reportable adverse events unless they occur in severity, frequency, or other manner that is significantly worse than the subject's baseline condition. Recurrence of AF, AFL, or AT will affect the primary effectiveness endpoint and should be reported on the Follow-Up Visit CRF.

Additionally, urinary tract infections (UTIs) that occur after a procedure and do not require a Foley catheter will not be considered adverse events. UTIs that require a Foley catheter will be reported as AEs if related to the procedure or meet serious criteria.

Unchanged, chronic, non-worsening or pre-existing conditions are not AEs and should not be reported.

All adverse events will be collected on each subject through the 15-month follow-up visit.

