#### 8.2.1 Primary Safety Endpoint Analysis

The primary safety endpoint will be summarized as the percentage of subjects who experienced one or more primary safety endpoints. The primary safety analysis population for the primary safety endpoint will be subjects in the primary analysis population who have completed their 7-day follow-up visit; or crossed the end of the 7-day visit window without the visit but with a primary safety endpoint event. Subjects without an event that are lost to follow up without a visit at or beyond their 7-day follow up visit window will be excluded from this analysis.

The primary safety endpoint event rate will be calculated based on the number of subjects experiencing a primary safety endpoint event divided by the total number of subjects in the analysis population. Relatedness of the event to the catheter and to the procedure will be determined by the independent physician reviewer.

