### 15.6 Steps Taken to Control or Mitigate Risks

In-depth recommendations, special precautions and instructions regarding patient selection, device handling, and device placement are included in the IFU. It is also stated in the IFU that the devices can only be used by physicians who have received appropriate training on how to use the device. This statement is interpreted to mean that the physician users are expected to be aware of the known and foreseeable safety risks associated with the use of the device including the surgical and/or non-surgical treatment of these conditions.

Risks associated with the use of the device under investigation are minimized through device design, investigator selection and training, pre-specified patient eligibility requirements, and study monitoring to ensure adherence to the protocol. All adverse events will be reported to the Sponsor as summarized in **Sections 7.1.1.1 - 7.1.1.4** and will be monitored internally for safety surveillance purposes.

**Device Design:** The catheter has a contact force magnetic sensor which plays an important factor in achieving transmural lesions that is critical in abolishing the substrate necessary for an arrhythmia and AF in particular. With increasing force, a greater proportion of the electrode surface area is in contact with the tissue, and there is more efficient energy coupling. Gaps in ablation lines are commonly seen when the amount of contact force over the RF delivery time is low and this is associated with higher recurrence rates after ablation for AF. Contact force-sensing ablation catheters such as TactiCath SE provide a valuable feedback mechanism to help ensure the efficacy of ablation.

**Investigator Selection and Training:** Investigators will be selected as outlined in **Section 10.1**. Sites will receive training as stated in **Section 10.3.1**. Additionally, ablating physicians will be qualified and have experience using a contact force sensor as stated in **Section 10.3.2**.

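### Section 7.1.1.1 gives two reporting rules for adverse events judged both non-serious and unrelated, so a listed safety event given both labels at the site may never reach the independent physicians

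*Combined protocol and SAP*

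**What the plan says.** Section 7.1.1.1 states the broad rule first: "All adverse event data, including deaths, will be collected throughout the time period defined above and will be reported to the Sponsor on a CRF". The same section then introduces a list with "For the purposes of this study, the following adverse events will be reported". The list has two items:

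- "Adverse events that are assessed by the investigator as being related to either the ablation catheter or the ablation procedure will be reported"
- "Serious adverse events, regardless of relatedness to the procedure and/or the ablation catheter will be reported as described in" Section 7.1.2.1.

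The paragraph on urinary tract infections applies the narrow rule: "UTIs that require a Foley catheter will be reported as AEs if related to the procedure or meet serious criteria". The section then closes with "All adverse events will be collected on each subject through the 15-month follow-up visit". Section 15.6 says "All adverse events will be reported to the Sponsor", and that sentence goes on to refer back to 7.1.1.1 and the sections after it.

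On the analysis side, Section 4.1.1 defines the primary safety endpoint as device- or procedure-related serious adverse events from a named list. Section 8.2.1 says "Relatedness of the event to the catheter and to the procedure will be determined by the independent physician reviewer". Appendix III says that its definitions are for the independent physicians, who determine whether a listed event is a related serious event belonging in the primary endpoint.

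**The concern.** With up to 15 sites, the plan leaves open what to do with an adverse event that the investigator considers neither serious nor related. One site can enter it under the opening sentence, and another can leave it out under the list. Both would be following Section 7.1.1.1.

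The second consequence concerns the primary safety endpoint. Two judgements make a listed event count: that it is serious, and that it is related to the catheter or procedure. Appendix III and Section 8.2.1 give these to physicians outside the trial. Under the narrow rule the site makes both judgements first, and an event that fails both is not reportable, so the independent physicians have nothing to overrule. The plan tests no hypothesis (Section 8.2), so the descriptive safety rate is itself the result. Section 1.1.2 says the data will be used together with those of the companion IDE trial to support a persistent AF indication.

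**Working it through.** The plan states no figure to reproduce, so the check is mainly a comparison of passages.

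**Step 1: do the two rules conflict?** The opening sentence of 7.1.1.1 covers both collecting and reporting on a CRF. A reading of 'collect everything, report some of it' therefore does not reconcile it with the list. There are four combinations of the site's calls:

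| Site's call | Opening sentence | List in 7.1.1.1 |
|---|---|---|
| Serious, related | Reported | Reported |
| Serious, unrelated | Reported | Reported |
| Non-serious, related | Reported | Reported |
| Non-serious, unrelated | Reported | Not reported |

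The rules differ in one cell only, the last.

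**Step 2: can that cell contain a primary endpoint event?** By Section 4.1.1 the endpoint counts only serious related events, so an event correctly placed in the last cell is not an endpoint event. The question is who decides that it belongs there. Appendix III names the independent physicians, but under the list the site's two calls settle it.

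**Step 3: which listed events could plausibly be placed there?** Some Appendix III definitions contain admission or intervention, which makes a non-serious call difficult: pulmonary edema, heart block, pneumothorax and major vascular complication. Others can be met without either:

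- transient ischemic attack, which resolves within 24 hours;
- thromboembolism, which includes deep vein thrombosis;
- pulmonary vein stenosis of at least 70% on CT or MRI.

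Stenosis is counted through 15 months (Section 4.1.1, note 1), so it may be found long after the procedure.

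**Step 4: size.** Section 8.2.1 defines the rate as subjects with at least one event divided by subjects in the analysis population. Taking about 100 subjects (Section 1.0) as the denominator, one subject whose only endpoint event is not reported changes the rate by 1/100 = 1 percentage point. A subject with another endpoint event that was reported changes it by nothing.

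As an illustration, assume 5 subjects truly have an event and 0 to 2 of them are lost in this way. Neither number is in the documents. Exact (Clopper-Pearson) 95% intervals are:

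| Subjects lost (assumed) | Reported rate | 95% interval |
|---|---|---|
| 0 | 5/100 = 5.0% | 1.6% to 11.3% |
| 1 | 4/100 = 4.0% | 1.1% to 9.9% |
| 2 | 3/100 = 3.0% | 0.6% to 8.5% |

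The shift is small against the sampling uncertainty, but it can go only one way.

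**The case against.** A reader might infer that the treating investigator's causality call filters the primary safety endpoint. The documents do not support that. SAEs are reported regardless of relatedness (7.1.1.1), Section 3.0 has all SAEs independently adjudicated, and 8.2.1 gives relatedness to the independent reviewer. A causality call alone cannot hide an endpoint event; the site must also call it non-serious.

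A reader might also take Section 15.6 as a second, independent broad rule. Read whole, its sentence defers to 7.1.1.1. The closing sentence of 7.1.1.1 can likewise be read as setting the duration of collection. The firm conflict is between the opening sentence and the list.

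There are other safeguards. Section 7.1.4 lets Safety personnel identify events for adjudication, Section 10.4 requires source documents that substantiate adequate adverse event reporting, and Section 10.3.1 trains all sites on the protocol and on CRF completion. These reduce the risk. They do not close it, because 7.1.4 names no data source from which an unreported event would be found, and training cannot settle a rule that the text states in two ways. The adjudication charter may say more, but it is not among the documents.

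Most endpoint events must also start within 7 days of an ablation, when a call of unrelated is hard to defend. That stands, and it is a reason to expect few affected subjects. It does not cover stenosis, which is evaluated through 15 months.

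Finally, the analyses visible in Section 8.2 include no pooled rate of non-serious events, so uneven capture of ordinary unrelated events distorts no result that can be seen. Restricting adverse event capture is also a legitimate choice in a post-market study. Both points stand. The difficulty is that the restriction is contradicted in the same section and includes no exception for the listed event types.

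**Conclusion.** The contradiction is certain but confined to events judged both non-serious and unrelated. Its route into the primary safety endpoint is narrow: a listed event given both labels at the site, and not picked up by Safety personnel, does not reach the physicians whom Appendix III charges with deciding on it.

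Any effect is toward a lower rate, about 1 percentage point per affected subject who has no other endpoint event. This assumes a denominator near 100. The number of such subjects cannot be found from the documents and may be zero, so the plan does not show that the safety rate is biased, only that it could be. The point should be corrected because the remedy is cheap and the descriptive rate is the study's main safety result. It does not threaten the design.

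**What to change.** Make the list in Section 7.1.1.1 the single reporting rule and add a third item: any suspected event of a type listed in Section 4.1.1 or Appendix III is reported, and sent for independent adjudication, whatever the investigator's judgement of seriousness or relatedness. Reword the opening and closing sentences of 7.1.1.1 so that they refer to that list, and change Section 15.6 to match. Section 8.2.1 needs no change, because it already says whose relatedness decision is analysed.

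The cost is protocol wording, an update to the CRF completion guidance, a few extra adverse event forms, and a safety rate that may come out slightly less favourable.

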#### 7.1.2 Serious Adverse Event (SAE) Reporting to Sponsor and IRB/EC

If the AE meets any of the criteria below, it is regarded as a serious adverse event (SAE).

- a) Led to a death,
- b) Led to a serious deterioration in health of the subject, that either resulted in
  1. a life-threatening illness or injury, or
  2. a permanent impairment of a body structure or a body function, or
  3. in-patient hospitalization or prolongation of existing hospitalization, or

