### 7.1.2.1 SAE Reporting

The investigator should report all SAEs to the Sponsor as soon as possible but no later than outlined below.

Clinical Site	Reporting timelines
All Sites	SAEs must be reported to the Sponsor no later than 3 calendar days from the day the site personnel became aware of the event or as per the investigative site's local requirements, if the requirement is more stringent than those outlined.

The date the site staff became aware the event met the criteria of an SAE must be recorded in the source document. The Investigator will further report the SAE to the local IRB/EC according to the institution's IRB/EC reporting requirements.

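### The exclusion of post-procedure UTIs without a Foley catheter from adverse events has no exception for serious cases, so a hospitalized case is an SAE under Sections 7.1.1 and 7.1.2 but not reportable under Section 7.1.1.1

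*Combined protocol and SAP*

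**What the plan says.** Section 7.1.1 defines the term broadly and without regard to relatedness: "An adverse event (AE) is any untoward medical occurrence, unintended disease or injury, or untoward clinical signs". Section 7.1.1.1 then sets out what is reported. Related AEs go into the database, and in addition "Serious adverse events, regardless of relatedness to the procedure and/or the ablation catheter will be reported".

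Later in Section 7.1.1.1 come two sentences on UTIs. The first says that "urinary tract infections (UTIs) that occur after a procedure and do not require a Foley catheter will not be considered adverse events". The second says that "UTIs that require a Foley catheter will be reported as AEs if related to the procedure or meet serious criteria".

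Section 7.1.2 begins its definition of an SAE with the words "If the AE meets any of the criteria below, it is regarded as a serious adverse event (SAE", and its list of criteria includes "in-patient hospitalization or prolongation of existing hospitalization" where this results from a serious deterioration in health. Section 7.1.2.1 adds: "The investigator should report all SAEs to the Sponsor as soon as possible but no later than outlined below". The limit given there is 3 calendar days from site awareness, or sooner if local rules are stricter.

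**The concern.** Seriousness is assessed only for something that already counts as an AE. A sentence that takes a whole class of events out of the AE category therefore also takes them out of the SAE category, however severe they are. The non-Foley UTI sentence does this. The words on serious criteria sit in the neighbouring sentence and apply only to the Foley group, so a site that follows the text closely would conclude that a hospitalized non-Foley UTI need not be reported.

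An event outside the AE category does not reach the later steps that depend on SAE status: the report to the sponsor, the onward report to the IRB/EC (Section 7.1.2.1), the sponsor's report to country authorities (Section 7.1.3), and the independent adjudication that Section 3.0 promises for all SAEs. With up to 15 sites in several countries, some may follow the UTI sentence and others the general definitions, so that the same event is recorded at one site and not at another. This matters for a study whose data are meant to support a persistent AF indication in China and other Asia Pacific countries (Section 1.1.2).

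**Working it through.** No figure in the plan bears on this and no sample-size or rate calculation applies. The check is to trace each kind of post-procedure UTI through the rules.

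**Step 1: the general rule.** Under Section 7.1.1 any UTI is an AE. Under the two bullets of Section 7.1.1.1 an AE is reported if it is related to the catheter or procedure, or if it is serious.

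**Step 2: the UTI sentences.** Foley UTIs are reported if procedure-related or serious, which is nearly the general rule restated. Non-Foley UTIs are not AEs at all.

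**Step 3: the two side by side, for non-Foley UTIs.**

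| Non-Foley UTI after a procedure | General rule (7.1.1, 7.1.1.1 bullets, 7.1.2) | UTI sentence (7.1.1.1) | Same answer? |
|---|---|---|---|
| Not serious, not related | Not reported | Not reported | Yes |
| Not serious, related | Reported as AE | Not reported | No, but plainly the purpose of the exclusion |
| Serious, not related | Reported as SAE | Not reported | No |
| Serious, related | Reported as SAE | Not reported | No |

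The second row is a deliberate and understandable choice to keep minor infections out of the database. The last two rows are the problem.

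**Step 4: does anything else restore the serious cases?** Foley use is not among the criteria in Section 7.1.2, so it cannot stand in for seriousness. The other exclusions in Section 7.1.1.1 have limits of their own. Arrhythmia recurrence becomes reportable when it is markedly worse than baseline, and the exclusion of existing conditions is aimed at those that have not worsened. Only the non-Foley UTI exclusion has no limit by severity. Section 15.2 lists infections among the anticipated device effects, so the plan does not treat infection as outside its safety interest. No section brings a serious non-Foley UTI back in.

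**Step 5: reach into the primary endpoint.** The components in Section 4.1.1 do not include UTI. Death is a component, but only when device- or procedure-related and with onset within 7 days of an ablation. Section 7.1.1.1 names deaths among the data collected on a CRF, and Section 5.5 requires the sponsor to be told of a discontinuation through death and keeps deceased/alive status even after withdrawal.

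**Step 6: scale.** The documents give no UTI rate. With about 100 subjects planned, each subject whose only SAE is an unreported UTI would lower a subject-level SAE proportion by 1/100, or 1 percentage point. How many such subjects there would be is unknown, and it may be none.

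**The case against.** The best answer is that there is no contradiction in strict logic. If a non-Foley UTI is not an AE, it cannot be an SAE, and the rule that all SAEs are reported is not broken: a specific carve-out overrides a general definition. Read that way, the direct clash is with the AE definition in Section 7.1.1, and the clash with the SAE rule follows only through it. This is fair as a reading, but it does not rescue the result. A carve-out that removes hospitalized infections from SAE reporting gives the wrong answer whether or not it is called a contradiction, and nothing in the text says that this was intended.

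The compliance statement also requires the most stringent applicable requirement to be followed, which favours reporting. It is generic, does not mention these sentences, and leaves each site to notice the problem. Section 7.1.4 lets safety staff as well as investigators identify events for adjudication, so site reporting is not the only route. That helps, but the section covers pre-specified events and does not say that UTIs are among them.

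A reader might infer several stronger things that the documents do not support:

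- *That fatal cases disappear.* Deaths are collected separately under Sections 7.1.1.1 and 5.5.
- *That septic cases disappear.* The exclusion names UTIs and not their complications. Sepsis fits the AE definition by itself and can be reported as its own event, although the plan does not say so expressly.
- *That a UTI is never an AE.* The exclusion covers UTIs after a procedure, and those between enrollment and the procedure remain reportable. The sentence sets no end date. A reading limited to the days around the procedure is plausible, but the gap exists under either reading.
- *That the primary safety rate is understated.* UTI is not a component. The Appendix III definition of death does refer to an adverse event, but to lose a death that way would need a related, fatal, non-Foley UTI with onset in the 7-day window and no separately reportable complication.

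**Conclusion.** The point holds for non-Foley UTIs after a procedure that meet a seriousness criterion, of which in-patient hospitalization is the clearest case. Sections 7.1.1 and 7.1.2 make such an event an AE and an SAE, the UTI sentence in Section 7.1.1.1 makes it neither, and the passages must be reconciled.

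The effect is on the completeness and consistency of SAE reporting and adjudication. The number of events is probably small, but that is a judgement: the documents give no basis for a figure. The primary safety rate changes little or not at all. The visible analyses are descriptive, with no hypothesis tests (Section 8.2) and no pass/fail criteria (Section 8.10), so no formal conclusion turns on this. It is still worth correcting, because a stated rule directs sites to leave out serious events.

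The conclusion assumes that sites apply the UTI sentence as written and that no separate document, such as CRF instructions or the adjudication charter, already restores these cases. Neither is available here.

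**What to change.** Add one clause to the end of the non-Foley UTI sentence in Section 7.1.1.1: *unless the event meets any seriousness criterion in Section 7.1.2, in which case it is reported as an SAE*. Minor UTIs stay excluded as the sponsor evidently wants, and in the table only the two serious rows change. The Foley sentence can stand.

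The cost is one clause, handled as a protocol amendment under Section 10.2, and at most a few extra SAE reports. It concerns reporting only and alters no treatment, visit or analysis.
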